HBB Prompt will be an interactive tool that guides frontline providers through the steps needed to save newborn babies at birth. HBB Prompt will facilitate individual and group training in health facilities using the Low Dose High Frequency model (LDHF) for resuscitation skills retention. Our group has successfully developed and tested a related application for the Neonatal Resuscitation Program (NRP), the newborn stabilization algorithm used in North America.(8) We will use lessons learned from our previous work to robustly develop HBB Prompt by integrating human factors and user-centered design approaches. We will engage end-users and HBB Master Trainers to iteratively collect feedback to develop HBB Prompt for both individual and small group resuscitation practice. Our iterative approach will mitigate the common scenario of mobile health (mHealth) solutions unable to achieve sustained success at scale due to lack of comprehensive input from frontline users. We will pilot the app at a single centre and compare it to a control site for HBB skills retention.

Hypothesis: Applying a user-centered design approach of collecting iterative qualitative data from end-users regarding learning needs and facilitators and barriers to HBB skills maintenance will enable creation of a mobile app that will improve skills retention in an intervention group versus a control group.

Objectives

1. To develop a refined HBB Prompt app through user-centered design involving input from frontline birth attendants in Uganda.
2. To train a minimum of twenty health workers from two district hospitals in Southwestern Ugandan in HBB 2.0 and Essential Care for Every Baby within 6 months of the start of the project.
3. To determine the impact of the HBB Prompt app on HBB skills retention of providers in the intervention site compared with providers in the control site (higher average OSCE B test scores) 12 months after training.

Objective 1: To develop a refined HBB Prompt app through user-centered design involving input from frontline birth attendants in Uganda.

Phase 1a

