We will train a minimum of 20 frontline health providers (10 per hospital) from two district hospitals in southwestern Ugandan in HBB 2.0 and ECEB. HBB and ECEB training will be conducted by national trainers in the ratio of 1 trainer to 6 providers. Providers will undergo ECEB training in addition to HBB as these training programs are recommended by the Uganda Ministry of Health to be offered together.

HBB 2.0 training takes place over one day and ECEB training over two days. Participants will be invited from both hospitals to any one episode of training to minimize the number of frontline birth attendants in trainings at any single time.

One hospital will be randomly selected and its providers will have access to the most updated version of HBB Prompt (beta) at the end of the trainings (Intervention arm). The control group will not have exposure to the HBB Prompt app post training.

Participants in both centers will be asked to achieve a minimum practice target of once per day. Our recommended frequency to use the app will be once per shift (i.e. run through 1 simulation per person as a pair). An HBB article from earlier this year showed the greatest improvement when health workers practiced at the beginning of every shift. As it may be difficult to ensure that it is done at the beginning of shift, we will leave the timing of once a shift practice at the discretion of providers. Whenever a new team comes on, they will be recommended to ask the previous team if they did a simulation practice. If not, then they will remind the outgoing team to complete it. These recommendations on frequency of practice will be offered at both the intervention and control sites. All sites will receive resuscitation practice mannequins and a resuscitation practice table.

We will present to the Health Facility team the results of their HBB simulation practice frequency as captured by the HBB Prompt app analytics in the intervention arm. This app analytics data on frequency of practice will be presented to the health facility every two months during the one year study period. The app will be designed to generate both individual and group (facility) practice frequency. Both intervention and control arms will have a standard log-book to record frequency of practice. The accuracy of the log-book will be compared to the data retrieved from app analytics in the intervention arm.

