Objective 3: To determine the impact of the HBB Prompt app on HBB skills retention of providers in the intervention site compared with providers in the control site.

1. Primary outcome: comparison of OSCE B scores in intervention (HBB Prompt) vs. control group. (17 out of 23 constitutes a pass score)
 - a. At 0 months, (immediately before and after training)
 - b. At 3 months
 - c. At 6 months (midline)
 - d. And at 12 months (endline)
2. Measures during the 12-month period of intervention in HBB Prompt site and control site at two unannounced visits (4 months, 9 months):
 - i. HBB 2.0 Knowledge check (18 questions)
 - ii. Bag and mask ventilation skills check (score out of 14)
 - iii. OSCE A (score out of 12, 9 out of 12 constitutes pass score)
 - iv. In addition to the OSCE skills checklist as scored by raters, we will use the Augmented Infant Resuscitator (AIR) to objectively measure quality of newborn resuscitation during every ventilation epoch. AIR records time stamped data on ventilation quality, such as presence of air leak or obstruction and ventilation rate (www.air-device.com).
 - b. Data on potential confounders will be collected for each site (volume of deliveries, workload in labor and delivery, burnout, motivation, baseline supervision, experience, previous training, provider level, number of patients/areas each provider is responsible for, length of time provider has been in practice, availability of equipment, availability of an HBB algorithm posted at the bedside.)
 - c. Other clinical outcomes will be collected from the Ministry of Health Birth Register: For each patient: date of birth, time of birth, birth weight, death before discharge, admission to nursery, 1 and 5 minute Apgar scores, resuscitation status at birth and resuscitation outcome.
 - d. Reports generated and presented to each site every 2 months: frequency of practice, number of deliveries, number of infants requiring bagging, fresh stillbirths, neonatal mortality in hospital
3. App analytics
 - a. Pattern of usage
 - i. Which components of the app are being used?
 - training mode, simulation mode, help videos, quizzes
 - b. Frequency (login, page use), purpose device ID
 - i. Is low dose high frequency happening? – Frequent, short duration access?
 - c. Self practice vs. peer or group practice
 - d. Trends for scores for simulations and quizzes

4. We will conduct exit focus group discussions and interviews at both intervention and control sites:

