 - a. For Intervention site providers:
 - i. Facilitators and barriers to implementing and maintaining HBB skills
 - ii. Did HBB Prompt help?
 - iii. Did HBB Prompt meet end-user needs
 - iv. Any suggestions for further improvement
 - v. Feasibility and sustainability of scale-up
 - vi. HBB Prompt specifics: content, interface, navigation, functionality, customizability, usability
 - b. For Control site providers:
 - i. Facilitators and barriers to implementing and maintaining HBB skills
 - ii. Discussion about ideas to facilitate skills maintenance
 - c. For both sites:
 - i. Perception of workload in labor and delivery, burnout, motivation
 - ii. Interviews only: description of baseline supervision, number of patients and areas each provider is responsible for, availability of equipment for practice and for clinical care (e.g. bag-mask ventilator, HBB algorithm)

Randomization

A random sequence generator will be used to determine a random number just prior to the start of phase 2. If the random number is odd, then Itojo will be the intervention site. If the number is even, then Kitagata will be the intervention site.

Study setting

Southwestern Ugandan (Itojo Hospital, Ntungamo District; Kitagata Hospital, Sheema District). Each study site will have HBB practice corners established and equipped with both resuscitation mannequins and resuscitation bag and mask devices.

Study duration

18 months in total, 4 months for phase 1 and 12 months for phase 2 and 2 months for data analysis.

Participant eligibility criteria and enrolment

Study Population Eligibility: We will conduct the study in an area where HBB is recommended as the training program for newborn resuscitation

Inclusion Criteria: Frontline birth attendants involved in the delivery or care of babies in the maternity ward, theater or pediatric wards with a possibility of involvement in newborn resuscitation.

Exclusion Criteria: Health workers providing care in other wards other than maternity and pediatrics.

Enrolment: Using community entry processes, the medical superintendents of each hospital will be approached and requested to allow the study to be conducted in the Hospital. Once consent is obtained from the superintendent, individual frontline birth attendants will be approached and consented to be part of the study before training sessions are conducted.

Data Analysis

Phase 1

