Audio recordings from focus groups and interviews will be transcribed. Transcripts will be reviewed for themes using a grounded theory approach. Data analyses will take place after each iteration of phase 1b to incorporate feedback to improve and adapt each version of the HBB Prompt prototype. At least two investigators will independently read all transcripts at least twice to obtain an overall understanding, identify data codes and ensure that all comments are carefully considered and included. Categories within the themes will then be identified, and any relationships among themes determined. As data are entered into the analyses, categories will continue to be generated, until there is no new data that cannot be categorized under existing codes. When this occurs, it is likely that a range of functions and features of an ideal mobile app as a learning tool for HBB will have been categorized. Further, we will also likely have categorized an assortment of barriers and facilitators to skills maintenance and implementation of HBB Prompt. A similar analytic approach has previously been successfully used in the development of an osteoporosis clinical decision support tool (10).

Phase 2

Comparison of intervention versus control for the following outcomes will be analyzed at each time point using the Mann-Whitney U test:

- Primary outcome: OSCE B score at 12 months
- Secondary outcomes:
 - OSCE B scores at 0, 3, and 6 months
 - At two unannounced site visits (months 4 and 9)
 - Knowledge check score
 - BMV skills check score
 - AIR data
 - Percentage of time with correct ventilation rate
 - Percentage of time with air leak during ventilation
 - Percentage of time with obstructed airway during ventilation
 - Time to effective ventilation
 - OSCE A score

Additionally, comparison of OSCE B score after training at 0 months and at 12 months within each arm using the Wilcoxon-signed rank test

	0 months	3 months	4 months	6 months	9 months	12 months
OSCE B	Pre/post HBB training	x		x		x
OSCE A			x		x	
Knowledge check			x		x	
Bag-mask skills			x		x	
AIR			x		x	

Descriptive statistics compared between intervention and control for:

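### With one hospital per arm, the planned test compares two hospitals and cannot separate the app's effect from the hospital's, so Objective 3 and the hypothesis claim more than the design can give

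*Protocol*

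**What the plan says.** - **Allocation.** Under Randomization, one random number decides which of two named district hospitals receives the app: odd for one, even for the other. Phase 2a (under Objective 2) sets a minimum of 10 providers per hospital.
- **Aim.** Objective 3 reads "To determine the impact of the HBB Prompt app on HBB skills retention of providers in the intervention site compared with providers" at the other hospital. The hypothesis expects "creation of a mobile app that will improve skills retention in an intervention group versus a control group".
- **Test.** Data Analysis, Phase 2: "Comparison of intervention versus control for the following outcomes will be analyzed at each time point using the Mann-Whitney U test". The primary outcome is the 12-month OSCE B score; the scores at 0, 3 and 6 months are secondary. Change from post-training to 12 months is tested only within each arm, with the Wilcoxon signed-rank test.
- **Pilot framing.** The opening section says: "We will pilot the app at a single centre and compare it to a control site for HBB skills retention".
- **Features that help interpretation.** Phase 2a mixes staff of both hospitals in the training sessions, gives both sites the same practice advice, and adds: "All sites will receive resuscitation practice mannequins and a resuscitation practice table". Under Objective 3, "Data on potential confounders will be collected for each site"; Data Analysis then compares these factors descriptively. The exit interviews and focus groups at both sites cover "Perception of workload in labor and delivery, burnout, motivation".

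Nowhere does the protocol say that the effects of app and hospital cannot be told apart.

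**The concern.** A Mann-Whitney p-value on provider scores treats the providers as independent units that differ systematically only by arm. Here every provider in an arm shares one hospital, with its own delivery volume, workload, supervision and equipment. The protocol itself lists these as potential confounders, so it expects that sites may differ on them. Any such difference at 12 months enters the primary comparison in full and cannot be told from an effect of the app.

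At stake is the trial's main conclusion. A small p-value would answer Objective 3 as worded, although the allocation supports a narrower statement. An analysis plan, which may exist but is not at hand, could not repair this, because no analysis creates a second hospital in either arm.

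**Working it through.** The protocol gives no significance level, power, effect size, SD or ICC, so there is no figure of its own to reproduce.

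**Inputs from the protocol:** 2 hospitals, 1 per arm; at least n = 10 providers per hospital; Mann-Whitney test of 12-month OSCE B.

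**Assumed:** two-sided 5% level; normal scores; ICC (share of total variance that lies between hospitals) from 0 to 0.20; n = 20 per hospital as a larger-enrolment case.

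**Step 1, from the allocation alone.** There are C(2,1) = 2 possible allocations. The smallest randomisation p-value is 1/2 = 0.50 one-sided and 2/2 = 1.00 two-sided. There are no between-hospital degrees of freedom within an arm, so the trial cannot estimate the ICC. This step needs none of the assumptions.

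**Step 2, variance.** In units of the total variance, the difference between arms, taken as an estimate of the app effect, has variance 2 × [ICC + (1 − ICC)/n]. Provider-level variation alone gives 2 × (1 − ICC)/n. The ratio is F = 1 + n × ICC/(1 − ICC). For n = 10:
- ICC 0.05: 1 + 10 × 0.05/0.95 = 1.53
- ICC 0.10: 1 + 10 × 0.10/0.90 = 2.11
- ICC 0.20: 1 + 10 × 0.20/0.80 = 3.50

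**Step 3, false-positive rate if the test is read as a test of the app.** The normal approximation is 2 × [1 − Φ(1.96/√F)]. The exact Mann-Whitney test was simulated with 100,000 trials per setting, one random hospital effect per arm and no app effect.

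| ICC | F, n = 10 | Normal approx., n = 10 | Simulated, n = 10 | Simulated, n = 20 |
|---|---|---|---|---|
| 0 | 1.00 | 5.0% | 4.4% | 4.8% |
| 0.05 | 1.53 | 11.3% | 9.4% | 15.8% |
| 0.10 | 2.11 | 17.7% | 14.5% | 25.6% |
| 0.20 | 3.50 | 29.5% | 25.1% | 40.2% |

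At n = 10 the simulated rate is 5.3% at ICC 0.01 and 6.3% at ICC 0.02, close to nominal. The exact test's own size at n = 10 is 4.3%.

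**Step 4, without an ICC.** Suppose the hospitals differ for reasons unrelated to the app by one-third, two-thirds or one within-hospital SD. Then p < 0.05 occurs in 10%, 26% and 52% of trials at n = 10.

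**Step 5, what the interval covers.** At n = 10 an ordinary 95% t interval covers the difference between these two hospitals about 95% of the time at every ICC. Read as an interval for the app effect, it covers 89%, 84% and 72% at ICC 0.05, 0.10 and 0.20.

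**Step 6, does a significant result still carry information?** At n = 10, the chance of p < 0.05 in favour of the app, with no app effect versus an effect of one total SD, is 3% v 52% at ICC 0.02, 7% v 54% at ICC 0.10, and 13% v 56% at ICC 0.20.

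**Step 7, change from the post-training score.** If the hospital effect is entirely stable over time, a between-arm comparison of change rejects in 4% to 5% of trials at ICC 0.05 to 0.20. Differences that arise during the 12 months remain.

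**The case against.** The strongest reply is that the protocol already presents a two-site pilot. The pilot sentence says so, Objective 3 names the comparison of intervention-site with control-site providers, a hypothesis states an expectation and not a permitted conclusion, and no significance level or efficacy claim is written down. This has weight, but it does not settle the matter. The pilot sentence does not say that app and hospital are inseparable, and the objective, the hypothesis and the primary test are worded as a question about the app's effect.

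Second, the design equalises a good deal: mixed training sessions, the same practice advice and the same equipment. The 0-month scores are also compared between arms. The relevant ICC may therefore be at the low end, where the error rate is near nominal. That is possible, but the trial cannot show it. The 0-month comparison can reveal a starting difference without removing it, and later divergence between the sites stays aligned with arm.

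Third, the sizes depend on an assumed ICC, an assumed level, normal scores for a bounded 23-point scale, and a larger enrolment that the protocol does not state. That is correct. The figures show a range and do not predict this trial's error rate. The structural point in step 1 does not depend on them.

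A reader might infer that a small p-value would fit an app effect and a mere hospital difference equally well, so that the result would be worthless. Nothing in the protocol supports that, and step 6 contradicts it for an effect of one SD: a significant result favouring the app is several times more likely with the effect than without it, even at ICC 0.20. Nor does it follow that enrolling more providers is harmful. More providers still improve precision; they worsen the error rate only if the test is read as a test of the app.

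**Conclusion.** The point holds. With one hospital per arm, the primary test addresses whether these two hospitals differ and cannot separate app from hospital. Objective 3 and the hypothesis claim more than that. This conclusion needs no assumed figures.

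Its size does. Under the stated assumptions and no app effect, the false-positive rate for the app reading at the minimum enrolment runs from about nominal (ICC 0.02 or below) to about 25% (ICC 0.20). Where this trial lies in that range cannot be learned from its data. A significant result would be evidence for the app weakened by an unknown amount.

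**What to change.** Keep the sites, the sample and the Mann-Whitney test.

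1. Reword Objective 3, both in the Objectives list and under its own heading, for example: *To obtain a preliminary pilot estimate of the difference in 12-month OSCE B score between the hospital given HBB Prompt and the control hospital.* Reword the skills-retention part of the hypothesis to match.
2. Add to Data Analysis, Phase 2: *Each arm is one hospital. Provider-level p-values and intervals describe the difference between these two hospitals, cannot separate app from hospital, and support no efficacy claim.*
3. Report the 12-month difference with a 95% interval labelled as the two-hospital difference, and name the estimator, since OSCE B is a bounded score and the planned test is rank-based.
4. Add a between-arm comparison of change from the post-training 0-month OSCE B score, or adjust the 12-month comparison for that score. The data are already collected. The change comparison removes hospital differences that are stable over time but not those that arise later, so the sentence in item 2 is still needed.

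An additional app-effect interval, widened over a range of assumed ICCs, is optional and not part of the required change.

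The cost is some rewording, one added sentence and a little more analysis, with no new sites or participants. The downside is a more modest permitted conclusion.

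### The primary 12-month OSCE B comparison leaves the post-training score unused, so precision is lost and a starting difference between the two hospitals goes unadjusted; adjustment would help only in part

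*Protocol*

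**What the plan says.** The Protocol (Data Analysis, Phase 2) names one between-arm method for all quantitative outcomes: "Comparison of intervention versus control for the following outcomes will be analyzed at each time point using the Mann-Whitney U test". First in the list under it is "Primary outcome: OSCE B score at 12 months".

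OSCE B is also scored at the start. Objective 3, item 1 lists "At 0 months, (immediately before and after training". App access follows training: for the selected hospital, "its providers will have access to the most updated version of HBB Prompt (beta) at the end of the trainings" (Phase 2a). The post-training score has two planned uses. One is a separate month-0 Mann-Whitney comparison, as a secondary outcome. The other is a "comparison of OSCE B score after training at 0 months and at 12 months within each arm using the Wilcoxon-signed rank test". Potential confounders are compared between arms descriptively only.

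Allocation is by hospital, from one random number: "If the random number is odd, then Itojo will be the intervention site" (Randomization); an even number selects the other hospital. On size, Phase 2a states "We will train a minimum of 20 frontline health providers (10 per hospital".

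**The concern.** Objective 3 asks whether providers with the app retain skill better. The natural reference for retention is the score each provider held on leaving training. The Protocol collects it, but no planned between-arm analysis of the 12-month score uses it.

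Two things are at stake. First, precision: at 10 providers per hospital, a covariate that explains part of the 12-month variance is left out at no saving. Second, starting differences: because hospitals and not providers are allocated, randomisation does not balance starting skill between arms. A gap present after training can carry into the 12-month comparison. The month-0 test may reveal such a gap but does not correct for it.

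**Working it through.** The Protocol gives no alpha, power, effect size, SD, intracluster correlation (ICC) or correlation between the two scores, so it has no power figure to reproduce. Its only size figure is 2 hospitals × 10 = 20 providers, a training minimum.

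**Inputs.** From the Protocol: 10 per arm, one hospital per arm, Mann-Whitney on 12-month OSCE B. Assumed: two-sided 5%, app effect 1 SD, correlation r = 0.3, 0.5 or 0.7 between post-training and 12-month score, no dropout, normal scores unless stated. Simulations used 20,000 trials per setting.

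**1. Precision, no hospital effect.** Adjustment multiplies the residual SD by √(1 − r²).

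| | r = 0.3 | r = 0.5 | r = 0.7 |
|---|---|---|---|
| 1 − r² | 0.91 | 0.75 | 0.51 |
| √(1 − r²) | 0.954 | 0.866 | 0.714 |
| Power, Mann-Whitney | 52.3% | 51.3% | 51.1% |
| Power, unadjusted t-test | 56.9% | 56.3% | 56.1% |
| Power, adjusted linear model | 58.3% | 65.7% | 82.0% |
| Mean 95% CI half-width, unadjusted (SD) | 0.93 | 0.93 | 0.93 |
| Mean 95% CI half-width, adjusted (SD) | 0.91 | 0.83 | 0.68 |

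Independent repeats gave about 50 to 51% for Mann-Whitney and 57%, 64 to 66% and 82% for the adjusted model. Adjustment alone is the step from t-test to adjusted model: 58.3 − 56.9 = 1.4, 65.7 − 56.3 = 9.4 and 82.0 − 56.1 = 25.9 points. The remaining 5 points or so come from replacing a rank test by a parametric one.

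**2. Ceiling at 23.** Scores were rounded and capped at 23, with assumed SD 3 and control means 19.5 post-training and 17.5 at 12 months. Power was 51 to 52% for Mann-Whitney and 56%, 64% and 79% for the adjusted model. With means 21.5 and 20, it was 47 to 48% against 50%, 56% and 69%. Type I error of the adjusted model stayed at 4.8 to 5.2% in both settings.

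**3. Starting gap of 0.5 SD (assumed), no app effect.** Rejection rates at r = 0.3, 0.5, 0.7:
- If the gap persists in full to 12 months: Mann-Whitney 16% throughout; adjusted model 11%, 9%, 7%.
- If it regresses to r × 0.5 SD: Mann-Whitney 5%, 8%, 10%; adjusted model 5% throughout.

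**4. Random hospital effect, no app effect.** With n per hospital, the variance of the difference in means is 2·ICC + 2(1 − ICC)/n, but a provider-level test sees only 2(1 − ICC)/n. At n = 10 and ICC 0.10 this is 0.20 + 0.18 = 0.38 against 0.18, a ratio of 2.11. The normal approximation to the error rate is 2[1 − Φ(1.96/√2.11)] = 17.7%; simulation of the exact Mann-Whitney gives 14.7%. For the adjusted model, the result depends on how far hospital effects at month 0 carry over to 12 months (r = 0.5 between providers):

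| ICC | Mann-Whitney | Adjusted, carry-over 0 | Adjusted, carry-over 0.5 | Adjusted, carry-over 0.9 |
|---|---|---|---|---|
| 0 | 4.2% | 5.0% | 4.9% | 5.1% |
| 0.05 | 9.3% | 13.3% | 10.2% | 7.1% |
| 0.10 | 14.7% | 21.1% | 15.1% | 10.0% |

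Across r = 0.3 to 0.7 at ICC 0.10, the adjusted model rejects in 18 to 30% with no carry-over, and in about 10% with carry-over 0.9.

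**The case against.** A rank test is a defensible choice for a bounded score in a small pilot, and it does compare the 12-month scores that Objective 3 names. Shared training sessions ("Participants will be invited from both hospitals to any one episode of training") may keep any starting gap small, and the 0.5 SD gap above is only an illustration. All of this stands, and it limits the size of the point.

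The strongest objection is that the power figures assume no hospital effect, the one case in which the allocation problem is absent. With both tests set to a true 5% level, ICC 0.10 and no carry-over, power for a 1 SD effect is about one third for either test, so the gain vanishes. With carry-over 0.9 the gain returns: roughly 42%, 52% and 69% against about 30 to 35%. The benefit thus depends on two unknowns, r and carry-over. This stands and belongs in the plan as a stated limit.

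The covariate is also scored after allocation, since the random number is drawn just before Phase 2 and training is part of Phase 2. The Protocol does not state that raters are masked. Scoring before app access protects the covariate from the app, but not from a rater who knows the allocation.

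An adjusted supplementary analysis could sit in an SAP that is not at hand. The primary test, however, is fixed in the Protocol itself.

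Two stronger readings are not supported. A reader might infer that the two within-arm Wilcoxon results will be set against each other as evidence of better retention; the Protocol lists them as additional and plans no such contrast. A reader might also infer that the post-training score is ignored altogether; it is used, but not in the primary comparison.

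**Conclusion.** The point holds as an improvement to consider. The primary comparison omits a score that is already collected and bears directly on retention. At 10 per arm, a 1 SD effect and no hospital effect, power rises from about 50% to about 57%, 65% or 82% at r = 0.3, 0.5 or 0.7. Of this, about 1, 9 and 26 points are due to adjustment, so the gain is negligible if r is low. A starting gap does less harm under adjustment but is not always removed.

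It would be wrong to infer that the planned Mann-Whitney test is sound at its nominal level and merely imprecise. It treats providers as independent when one hospital per arm is allocated, and its error rate is about 9% at ICC 0.05 and 15% at ICC 0.10. It would be equally wrong to infer that adjustment cures this: the app and the hospital remain confounded under either test, and without carry-over the adjusted test is the worse of the two for false positives. The correlation, ICC, carry-over, effect size and alpha are all assumptions. Confidence is medium.

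**What to change.** Amend Data Analysis, Phase 2 as follows:

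- Name one primary analysis, with no data-dependent switch: a linear model of 12-month OSCE B on arm with post-training month-0 OSCE B as covariate. Report the adjusted mean difference and 95% CI, which fits the average-score wording of Objective 3.
- State that the post-training OSCE B is scored before app access.
- Keep the unadjusted Mann-Whitney test as a sensitivity analysis.
- Label the within-arm Wilcoxon tests as descriptive.
- State the limits: with one hospital per arm, no provider-level analysis separates app from hospital or guarantees the 5% level. The adjusted test can reject a true null more often than Mann-Whitney if hospital effects do not carry over from month 0. The p-value and CI are to be read as conditional on these two hospitals.

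The cost is analysis wording only; both scores are already in the assessment schedule. The price in inference is the possible rise in false positives just described.

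### Objective 3 is worded as a higher average OSCE B score, but the only planned between-arm analysis is a Mann-Whitney U test, which gives no difference in points

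*Protocol*

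**What the plan says.** The protocol touches this point in three places.

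- **Objectives, item 3.** The app's impact on skills retention is to be judged against the "control site (higher average OSCE B test scores) 12 months after training".
- **Objective 3, item 1.** The entry reads "Primary outcome: comparison of OSCE B scores in intervention (HBB Prompt) vs. control group", followed by a bracketed note that "17 out of 23 constitutes a pass score". The proportion passing is not named as an outcome.
- **Data Analysis, Phase 2.** Between-arm outcomes "will be analyzed at each time point using the Mann-Whitney U test", headed by "Primary outcome: OSCE B score at 12 months". OSCE B after training is also compared with OSCE B at 12 months, "within each arm using the Wilcoxon-signed rank test". The list of descriptive comparisons covers demographics and confounders, clinical outcomes and practice frequency. It does not include OSCE B means or pass counts.

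One hospital is allocated to each arm (Objective 2, Phase 2a; Randomization), with a training minimum of 10 providers per hospital.

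**The concern.** The objective names its measure of success, the average score. The analysis section names its method, a rank test. The two do not match. A Mann-Whitney test asks whether providers in one arm tend to rank above those in the other. It does not say by how many points the averages differ, or how precisely that difference is known. The signed-rank test cannot fill the gap, because it compares each arm with itself.

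For a two-site pilot, the size of the effect in points and its uncertainty are what a later study would most need. The protocol's background stresses that skills decay after training. If decay is uneven, so that most providers stay near the top and a few fall far, a rank test gives those few little weight: a score of 8 counts no more than any other score at the bottom of the ranking. The mean reflects how far they fell, and a count at the pass mark shows how many fell below it.

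**Working it through.** The protocol gives no power, effect size, SD or significance level, so there is no stated figure to reproduce. The check asks whether rank order and mean can disagree on this scale at this size, and how often.

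**Inputs.** From the protocol: scores out of 23, pass mark 17, at least 10 providers per arm. Assumed for illustration: the score patterns below, exactly 10 per arm, and a two-sided 5% level.

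**Constructed example 1.**
- App: 19, 19, 20 (six times), 21, 21. Sum 200, mean 20.0, median 20, passes 10 of 10.
- Control: 8, 9, 10, 21, 21, 21, 22, 22, 22, 22. Sum 178, mean 17.8, median 21, passes 7 of 10.
- Difference in means: 20.0 − 17.8 = 2.2 points in favour of the app.
- Pairs: 10 × 10 = 100. App wins: 10 × 3 low control scores = 30. Ties: two app 21s × three control 21s = 6. App losses: 100 − 30 − 6 = 64.
- Strict wins 30/100 = 30%. With ties as half: (30 + 3)/100 = 33%. Ranks lean towards control.
- Mann-Whitney p = 0.20.
- Welch interval: sums of squared deviations are 4.0 (app) and 335.6 (control), so the variances (divided by 9) are 0.444 and 37.29. SE = √(0.444/10 + 37.29/10) = 1.94; df = 9.2; t = 2.254. The 95% CI is 2.2 ± 2.254 × 1.94, or −2.2 to 6.6 (p = 0.29).
- A percentile bootstrap on the same data gave about −1.3 to 6.0, a width of 7.3 against 8.8 for Welch. It is too narrow at this size.
- Passes 10/10 v 7/10: Fisher p = 0.21.

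Mean and rank order point in opposite directions, and all three tests are inconclusive.

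**Constructed example 2, an extreme case.**
- App: 20, 20, 20, 21, 21, 21, 21, 22, 3, 4 (mean 17.3, 8 passes).
- Control: 17, 17, 18 (five times), 19, 19, 19 (mean 18.1, 10 passes).
- App wins 8 × 10 = 80 of 100 pairs, with no ties. Mann-Whitney p = 0.024 (exact 0.020) favours the app, while the mean favours control by 0.8 points.

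A significant reversal can therefore be built, but it needs two providers at 3 and 4 while the other eight outscore every control.

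**How often.** Rounded normal scores, assumed control mean 15 and SD 3, pure shift between arms, 10 per arm, 5,000 simulated trials per setting:

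| True shift (points) | Mean and ranks opposite in sign | Opposite in sign with p < 0.05 |
|---|---|---|
| 0 | 5.5% | 0 |
| 2 | 1.5% | 0 |
| 3 | 0.4% | 0 |
| 4 | 0.04% | 0 |

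Simulations with uneven decay gave opposite signs in about 6–12% of trials, again never with p < 0.05. That range depends on the decay pattern assumed.

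**The case against.** The strongest reply is that a rank test is a sound choice for a bounded checklist score with about 10 providers per arm. The word average occurs once, in a bracket; elsewhere the protocol speaks only of comparing scores, and a Mann-Whitney test does that. Effect estimates and intervals are commonly left to an SAP, and none is shown here. Replacing the rank test would be a preference, and a provider-level interval could suggest more precision than two hospitals can give.

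Much of this stands. The Mann-Whitney test is defensible and should stay. The lack of an interval would not by itself be a finding. What remains is that the protocol fixes both a target and a method, and the method does not estimate the target. An SAP that follows this text would inherit the mismatch. The point about hospitals is correct and belongs in the fix: with one hospital per arm, variation between hospitals cannot be estimated by any method.

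A reader might infer two stronger things. One is that the primary test is likely to contradict the objective. The simulations do not support that, and the protocol gives no score distribution that would. The other is that a promised pass-rate analysis is missing. The 17-of-23 mark describes the instrument, as the 9-of-12 mark does for OSCE A, and is nowhere declared an endpoint.

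**Conclusion.** The point holds in a limited form. The objective is stated as an average, the sole between-arm analysis is rank-based, and no listed analysis or summary gives the OSCE B means or their difference. The main reason to act is that the plan as written does not estimate the quantity the objective names. A reversal of sign is a secondary reason. It is possible at 10 per arm, but it was uncommon in simulation (0.04% to 5.5% under a pure shift, about 6–12% under uneven decay) and never significant there.

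These figures rest on assumed score distributions and on exactly 10 providers per arm, which the protocol gives only as a minimum. The conclusion about the wording does not depend on them. The documents do not support calling the Mann-Whitney test wrong, or saying that it has no bearing on the average: when the arms differ mainly by a shift, the two nearly always agree in direction.

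**What to change.** In Data Analysis, Phase 2:

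1. Keep the Mann-Whitney U test for OSCE B at 12 months.
2. Add the between-arm difference in mean 12-month OSCE B, in points, with a Welch 95% CI. A percentile bootstrap is not recommended at this size.
3. Add the number per arm scoring at least 17 of 23 at 12 months, labelled as a descriptive summary.
4. State that, with one hospital per arm, the interval reflects variation between providers only and not between hospitals, so it does not express the full uncertainty about the app's effect.

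This needs no new data, only wording and a few lines of analysis. The downside is that the interval will be wide: in example 1 it spans 8.8 points of a 23-point scale.
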